8.3.1 Minimal disease activity (MDA)

MDA is a state of disease activity deemed a useful target of treatment by both the patient and physician, given current treatment possibilities and limitations. Criteria shown in Table 8-4 covering all of the domains of the disease have been developed to determine whether or not patient has reached MDA based on key outcome measures in PsA. A subject is considered as having MDA if 5 or more of the following 7 criteria in Table 8-4 are fulfilled:

Table 8-4: MDA criteria in PsA

A subject is classified as in MDA when they meet 5 of 7 of the following criteria:
TJC \leq 1
SJC \leq 1
PASI \leq 1 or BSA \leq 3
PtAAP \leq 15
PGADA \leq 20
HAQ-DI \leq 0.5
Tender enthesial points \leq 1

BSA=body surface area; HAQ=Health Assessment Questionnaire; MDA=minimal disease activity; PASI=Psoriasis Area and Severity Index; PGADA=Patient’s Global Assessment of Disease Activity; PtAAP=Patient’s Assessment of Arthritis Pain; SJC=swollen joint count; TJC=tender joint count

Following rule will be applied for subjects with BSA < 3 at Baseline due to missing post-Baseline measurements for BASI and PASI: Subjects with BSA < 3 will always meet the criteria PASI ≤ 1 or BSA ≤ 3.

The MASES items will be used to check whether a subject has less or equal one tender enthesial point.

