8.1.1.1 Tender joint count (TJC) and swollen joint count (SJC)

8.1.1.1.1 78/76 joint evaluation for ACR response

The Principal Investigator, another delegated physician, or an appropriately qualified medical professional (based on local requirements) who has had documented training on how to perform these assessments correctly assesses the following joints for tenderness: the distal interphalangeal, proximal interphalangeal and metacarpophalangeal joints of the hands, and metatarsophalangeal joints of the feet, the carpometacarpal and wrist joints (counted separately), the elbows, shoulders, acromioclavicular, sternoclavicular, hip, knee, talo-tibial, and midtarsal joints. All of these except for the hips are assessed for swelling.

Artificial and ankylosed joints, as well as missing joints (ie, amputated joints), are excluded from both tenderness and swelling assessments.

One dactylitic digit is to be counted as 1 swollen joint (instead of counting as 3 in the finger or 2 in the toe).

[Table 8–1](#) summarizes the swelling and tenderness grading criteria.

Table 8–1: Swelling and tenderness grading

The tender joint counts (TJC) and swollen joint counts (SJC) are weighted joint counts. If there are missing observations in the tender or swollen joint assessments, then the remaining observations will be assessed and weighted by the number of the assessed joints (AJ):

$$SJC = n * \sum_{i=1}^n SJ / \sum_{i=1}^n AJ \tag{9}$$

$$TJC = n * \sum_{i=1}^n TJ / \sum_{i=1}^n AJ \tag{10}$$

where n is the number of total joints. If a joint is missing at Baseline, then that joint is set to missing throughout the study. If more than 50% of the tender joint assessments or 50% of the

swollen joint assessments are missing at the time of a given assessment, then no imputation will be done and the total TJC or SJC will be set to missing for that visit.

Injected joints will be counted as swollen and tender from the date of injection up to 52 weeks after injection, ie, swelling and tenderness grading is 1.

8.1.1.1.2 28 joint evaluation for determination of DAS28(CRP)

The following 28 joints will be used for calculation of the DAS28(CRP).

- Upper extremity (26)-bilateral shoulders, elbows, wrists (includes radiocarpal, and carpal and carpometacarpal bones considered as a single unit), MCP I, II, III, IV, and V, thumb interphalangeals (IP), PIP II, III, IV, and V
- Lower extremity (2)-knees

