8.3.1.1 Modified MDA

Subjects are classified as in modified MDA when they meet the criteria PASI ≤ 1 or BSA ≤ 3 and 4 of the following criteria: TJC ≤ 1, SJC ≤ 1, PtAAP ≤ 15, PGADA ≤ 20, HAQ-DI ≤ 0.5 or tender enthesial points ≤ 1. The difference between the MDA and the modified MDA is that the PASI/BSA criteria is a mandatory criteria.

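### MDA and modified MDA test TJC ≤1 and SJC ≤1 on prorated counts, so one affected joint plus any non-assessed joint fails the criterion

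*SAP*

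**What the plan says.** SAP 8.3.1 sets the rule: "A subject is considered as having MDA if 5 or more of the following 7 criteria" are met. Its Table 8-4 repeats it, "A subject is classified as in MDA when they meet 5 of 7 of the following criteria", and lists TJC ≤1 and SJC ≤1 among the seven. SAP 8.3.1.1 makes the skin criterion mandatory and asks for four of the remaining six, with the same cut-offs: "TJC ≤ 1, SJC ≤ 1, PtAAP ≤ 15" and so on. Neither section defines the counts, refers to an unweighted count or gives a rounding rule. Table 9-3 in Protocol 9.10 states the two criteria simply as joint counts of at most 1.

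The counts are defined in SAP 8.1.1.1: "The tender joint counts (TJC) and swollen joint counts (SJC) are weighted joint counts". When joints are missing, "the remaining observations will be assessed and weighted by the number of the assessed joints". The multiplier is n, "where n is the number of total joints", and SAP 8.1.1 gives 78 for tenderness and 76 for swelling. Artificial, ankylosed and amputated joints are not assessed. In addition, "If a joint is missing at Baseline, then that joint is set to missing throughout the study". If more than half of the joints are missing, the count itself is set to missing. An injected joint is scored tender and swollen for up to 52 weeks.

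For the enthesitis criterion, SAP 8.3.1 adds: "The MASES items will be used to check whether a subject has less or equal one tender enthesial point". Joints have no comparable sentence.

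**The concern.** Proration suits percentage improvement and change from Baseline, where a fractional count does no harm. It does not suit a cut-off at exactly 1. A count of one affected joint is a whole number only when every joint has been assessed. Otherwise it lands just above 1 and fails. For a subject with any non-assessed joint, the criterion then means no affected joints at all, which is stricter than Protocol Table 9-3.

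A joint missing at Baseline stays missing, so the subject carries the stricter criterion through the study. The injected-joint rule adds a second route: a subject whose only counted joint is one injected as rescue scores 1 on both counts and meets both criteria if all other joints are assessed, but fails both if one other joint is not.

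At stake is the accuracy of the MDA and modified MDA frequency tables. MDA is also tabulated in the Week 12 interim analysis (SAP 4.3.1).

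**Working it through.** The plan states no figure for this point, so there is none to reproduce.

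**Inputs.** Joint totals n = 78 (TJC) and n = 76 (SJC), from SAP 8.1.1. Proration from SAP 8.1.1.1, equations 9 and 10: count = n × (affected joints) / (assessed joints). Cut-off ≤1, from SAP 8.3.1 and 8.3.1.1. Proration applies up to 50% missing, from SAP 8.1.1.1.

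**Step 1: one affected joint, m joints not assessed.** The count is n / (n − m).

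| m | TJC | SJC | ≤1 as written | Rounded to nearest integer |
|---|---|---|---|---|
| 0 | 78/78 = 1.000 | 76/76 = 1.000 | met | 1, met |
| 1 | 78/77 = 1.013 | 76/75 = 1.013 | not met | 1, met |
| 2 | 78/76 = 1.026 | 76/74 = 1.027 | not met | 1, met |
| 5 | 78/73 = 1.068 | 76/71 = 1.070 | not met | 1, met |
| 10 | 78/68 = 1.147 | 76/66 = 1.152 | not met | 1, met |
| 25 | 78/53 = 1.472 | 76/51 = 1.490 | not met | 1, met |
| 26 | 78/52 = 1.500 | 76/50 = 1.520 | not met | 2, not met |
| 50% | 78/39 = 2.000 | 76/38 = 2.000 | not met | 2, not met |

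**Step 2: other numbers of affected joints.** With none affected, the count is n × 0 / (n − m) = 0 and the criterion is met for any m. With two or more affected, the count is at least 2 and the criterion fails with or without proration. Only subjects with exactly one affected joint are touched.

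**Step 3: direction.** Since n / (n − m) ≥ 1, the prorated count is never below the observed count. Compared with the observed count, proration can turn a met criterion into an unmet one and never the reverse.

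**Step 4: effect on the classification.** MDA changes only if the subject would otherwise have met enough of the seven criteria and this failure takes the total below five. Modified MDA changes only if the skin criterion is met and the failure takes the other six below four.

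**Step 5: size, by assumption only.** The documents do not say how many subjects have a non-assessed joint, or how many of those have exactly one affected joint at a visit. If the first share were 5–20% and the second 10–20%, a joint criterion would be misjudged in 0.05 × 0.10 = 0.5% to 0.20 × 0.20 = 4% of subjects. With 40 subjects per arm, that is 0.2 to 1.6 per arm at a visit. These are subjects with a misjudged criterion; those whose MDA status changes are a subset.

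**The case against.** The strongest objection is that the SAP never says MDA uses the prorated count. Equations 9 and 10 stand under a heading about the joint evaluation for ACR response, and 8.3.1 does not refer to them. So the gap may be only a missing link between two sections. This lowers certainty about what would be programmed. It does not remove the point, because the SAP gives no other rule for forming the TJC and SJC totals and 8.3.1 uses the same terms without redefinition. If another count was intended, 8.3.1 still has to say so.

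One could also read n as the joints that can be assessed in that subject, so that permanently excluded joints would not inflate the count. The text says total joints, and under that reading a joint missed at a single visit would still push the count above 1.

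The enthesitis sentence is weak support. It may simply name the data source for a criterion that Table 8-4 does not otherwise define, and the SAP does not present it as a way round proration.

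It is also fair that an estimate above 1 is what proration is meant to produce when many joints went unexamined. That stands, and is a reason to prefer rounding to the raw count, which would let a subject with only 38 of 76 joints examined pass with one swollen joint.

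Finally, little depends on MDA. It is one of the other efficacy variables, summarised in frequency tables by visit (SAP 8.3), and plays no part in the testing sequence or the sample size. This also stands.

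**Conclusion.** The point holds as a minor one. As SAP 8.1.1.1, 8.3.1 and 8.3.1.1 are written, a subject with exactly one tender (or exactly one swollen) joint and at least one non-assessed joint has a count of at least 1.013 and fails that criterion. This rests on TJC and SJC in 8.3.1 being the counts defined in 8.1.1.1. The consequence runs one way, towards fewer responders. The effect on MDA rates cannot be computed from the documents and is probably small; the range in the working rests on assumed shares and is not an MDA rate. The primary ACR50 analysis and the secondary variables are unaffected.

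A reader might infer three stronger things that the documents do not support:

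- That MDA is understated for every subject with a non-assessed joint. Subjects with no affected joint, or with two or more, are classified as they would be without proration.
- That the misclassification repeats at every visit. Baseline missingness persists, but the error needs exactly one affected joint at that visit and a decisive criterion.
- That differences from placebo are diluted. That depends on how many subjects in each arm have a single residual joint, which the documents do not give.

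**What to change.** In SAP 8.3.1 and 8.3.1.1, add that for the ≤1 criteria the prorated TJC and SJC are rounded to the nearest integer, with halves rounded up (the tie arises at TJC = 78/52 = 1.5). Leave equations 9 and 10, the injected-joint rule and the rule for more than 50% missing joints unchanged.

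One affected joint then meets the criterion with up to 25 joints not assessed, a count with heavier missingness still fails, and two affected joints always fail. Rounding is not interchangeable with using the observed count: the two differ from 26 non-assessed joints upward.

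The cost is one sentence in each section and one line of derivation code. The small downside is that a few non-assessed joints are not counted against the subject.

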## 8 STUDY PROCEDURES BY VISIT

The Schedule of Study Assessments (Table 5–1) provides a general overview of study assessments. A list of procedures to be completed at each visit is described below.

Visit windows are +/-3 days from Baseline (Day1, first dose of IMP) at all visits through the Week 12 Visit and +/-4 days for all visits after Week 12 except the SFU Visit. For the SFU Visit (20 weeks after the last dose), the visit should occur no more than 3 days prior to the scheduled visit date and within 7 days after the scheduled visit date (-3 days/+7 days). The minimum time between doses during the Double-Blind Period should be no less than 25 days and no more than 31 days and during the Dose-Blind Period should be no less than 24 days and no more than 32 days. Changes to the dosing schedule outside of the allowed windows must be discussed with the Medical Monitor and may result in subject withdrawal.

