### **8.3.5 Week 12 (+/-3 days)**

The following procedures of assessments will be completed prior to administration of IMP:

- Record concomitant medications.
- Record AEs.
- eC-SSRS
- HADS
- Administer the PsAQoL.
- Determine the BASDAI.
- Administer the HAQ-DI.
- Administer the SF-36.
- Administer the PGADA.
- Administer the PtAAP.
- Administer the PsAID-9.
- Administer the tuberculosis questionnaire.
- Measure temperature, pulse, and BP.
- Measure weight.
- Perform a physical examination, including an evaluation for signs and symptoms of active TB and risk for exposure to TB.
- Perform TJC/SJC.
- Determine BSA affected by PSO using the BSA palm method.

- 
- If the BSA affected by PSO was  $\geq 3\%$  at Baseline/Day 1, determine the PASI.
  - Determine the mNAPSI.
  - Determine the MASES.
  - Determine the LDI.
  - Perform the PhGADA.
  - Perform an ECG.
  - Collect samples for hematology/biochemistry/urinalysis.
  - Collect blood sample for hs-CRP and CRP.
  - If there has been a delay in menses, perform a urine pregnancy test.
  - Collect a blood sample for bimekizumab plasma concentrations and anti-bimekizumab antibody detection.
  - Collect blood samples for cytokines, complement, and biomarker analyses.
  - For consenting subjects:
    - Collect blood samples for genomic and proteomic/metabolomics analyses.
    - Collect blood sample for genetic/epigenetic analysis.
  - For participating centers, collect blood sample for flow cytometry.
  - Record visit in the IXRS.
  - Administer IMP (bimekizumab).

The following procedures of assessments will be completed following administration of IMP:

- Collect pulse and BP once after dosing.

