## 9 ASSESSMENT OF EFFICACY

The ACR50 response at Week 12 is the primary efficacy variable. In addition the ACR20 and ACR70 responses are secondary or other efficacy variables. Several assessments must be completed in order to determine the ACR response. These include the TJC and SJC based on 78 and 76 joints, respectively, PGADA, PhGADA, PtAAP, HAQ-DI, and CRP. The methods for the component measures will be described first, followed by ACR response and assessments used in secondary and other efficacy variables.

The timing for all assessments is specified in the Schedule of Assessments (Table 5–1).

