## 9.8 BSA-PSO

The BSA palm method will be used for the evaluation of BSA affected by PSO as follows:

The subject's hand, including the palm, fingers and thumb, is used as the reference point for measuring how much of their skin is affected by psoriasis, representing roughly 1% of the body's surface.

- Subject's palm=1%
- Head and neck=10% (10 palms)
- Upper extremities=20 % (20 palms)
- Trunk=30% (30 palms)
- Lower extremities=40 % (40 palms)

Total BSA=100%

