## 9.9 Psoriasis Area and Severity Index (PASI)

PASI will be assessed in all subjects with Baseline/Day 1 BSA affected by PSO  $\geq 3\%$  determined by the method described in Section 9.8 (ie, the BSA palm method).

The PASI is the most commonly used and validated assessment for grading the severity of psoriasis in clinical studies (Feldman, 2004). The PASI quantifies the severity and extent of the disease and weighs these with the percentage of BSA involvement.

The percent area of involvement (BSA%) is estimated across 4 body areas; head, upper limbs, trunk, and lower limbs and then transferred into a grade (Table 9-2).

The Investigator assesses the average redness, thickness, and scaliness of lesions in each body area (each on a 5-point scale); 0=none, 1=slight, 2=moderate, 3=marked, and 4=very marked.

The PASI score ranges from 0 to 72 with a higher score indicating increased disease severity.

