**Table 9–2: Body areas for calculation of percent BSA for PASI**

Body area	Details of area	BSA	Degree of involvement of body area a
Head	Face, back of head	10%	0 to 6
Upper limbs	Left, right, upper lower, flexor surface, extensor surface	20%	0 to 6
Trunk	Front, back, groin	30%	0 to 6
Lower limbs	Left, right, upper lower, flexor surface, extensor surface, including buttocks	40%	0 to 6
Total		100%	

BSA=body surface area; PASI=Psoriasis Area and Severity Index

a Where 0=none; 1=1% to <10% affected, 2=10% to <30% affected, 3=30% to <50% affected, 4=50% to <70% affected, 5=70% to <90% affected, 6=90% to 100% affected

The PASI75, PASI90, and PASI100 responses are based on at least 75%, 90%, and 100% improvement in the PASI score. PASI will be assessed at Screening and at Baseline/Day 1. Thereafter PASI will be assessed for the purposes of determining response only in subjects with psoriasis involving at least 3% of body surface area at Baseline/Day 1.

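### SAP 8.3.1 scores the MDA skin criterion as met for every subject with Baseline BSA below 3%, including at visits where the protocol lists a BSA measurement (low impact)

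*SAP*

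**What the plan says.** SAP 8.3.1 defines MDA as at least 5 of 7 criteria, one of which is the skin criterion, PASI ≤1 or BSA ≤3. For subjects whose Baseline BSA is below 3 it adds a special rule, "due to missing post-Baseline measurements for BASI and PASI: Subjects with BSA < 3 will always meet the criteria". BASI is evidently a misprint for BSA. The rule names no visits and is not conditional on BSA being absent. SAP 8.3.1.1 defines modified MDA as the skin criterion, now mandatory, plus 4 of the other 6. It states no separate rule for low Baseline BSA.

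The protocol treats PASI and BSA differently. Section 9.9 restricts PASI by Baseline BSA: "Thereafter PASI will be assessed for the purposes of determining response only in subjects with psoriasis involving at least 3% of body surface area". Section 9.8 on BSA carries no such restriction: "The BSA palm method will be used for the evaluation of BSA affected by PSO as follows". The Week 12 list (Section 8.3.5) says "Determine BSA affected by PSO using the BSA palm method", with no Baseline condition, and its next item makes PASI conditional on Baseline BSA ≥3%. The lists for Week 24, Week 48, Early Termination and Safety Follow-Up pair the two items in the same way.

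**The concern.** The reason given for the rule and the rule itself do not cover the same visits. The reason is missing data. The rule applies at every visit, including those where the protocol asks for BSA in everyone. A programmer who follows the word 'always' would set aside an observed BSA above 3% and score the skin criterion as met.

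Compared with scoring from observed BSA, this can only raise MDA and modified MDA rates. It matters more for modified MDA, whose only difference from MDA is that skin is mandatory: for these subjects the mandatory component becomes automatic. It also sits badly with SAP 8.3, which analyzes such binary variables on observed cases with non-responder imputation.

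**Working it through.** The documents state no MDA rate, so there is no figure to reproduce. The check has two parts.

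**1. Where does the missing-data reason hold?** The documents do not list the MDA table visits. I took the post-Baseline visits in protocol Section 8 that include MASES, which supplies the tender enthesial points.

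| Visit | BSA listed for all subjects | PASI when Baseline BSA <3% | Reason holds for BSA? |
|---|---|---|---|
| Weeks 4, 8, 16, 36 | No | Not collected | Yes |
| Weeks 12, 24, 48 | Yes | Not collected | No |
| Early Termination, Safety Follow-Up | Yes | Not collected | No |

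Of the 4 + 3 = 7 scheduled treatment visits, the reason fails at 3. Early Termination is not a separate analysis visit, because SAP 3.5 maps its data to a scheduled visit. Safety Follow-Up is 20 weeks after the last dose. Weeks 2 and 20 collect five other MDA components but neither MASES nor BSA, so the reason holds there for BSA as well.

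**2. What changes when an observed BSA >3% is scored as met?** Let k be the number of the other 6 criteria that are met. There are 2^6 = 64 pass/fail patterns.

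- Skin forced to met: MDA needs k + 1 ≥ 5, so k ≥ 4. Patterns: C(6,4) + C(6,5) + C(6,6) = 15 + 6 + 1 = 22. Modified MDA also needs k ≥ 4, giving 22.
- Skin scored as not met: MDA needs k ≥ 5. Patterns: 6 + 1 = 7. Modified MDA cannot be reached, giving 0.
- Fail to pass: MDA 22 − 7 = 15 patterns, all with k = 4. Modified MDA 22 − 0 = 22 patterns, with k = 4, 5 or 6.

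These are counts of patterns, not probabilities. They show which subjects can change, not how many will. A change needs all of the following: Baseline BSA <3%, a later BSA >3%, a visit where BSA was measured, and k in the stated range.

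**The case against.** **The schedule table is not visible.** Protocol Section 9 says "The timing for all assessments is specified in the Schedule of Assessments", that is, in Table 5-1, and the copy of that table in the SAP is broken. A footnote limiting post-Baseline BSA cannot be excluded, and the SAP authors, who had the table, describe these measurements as missing. The lists are not flawless either: Section 9.9 places PASI at Screening, but the Screening list omits it. Against this, protocol Section 8 calls the table a general overview and introduces the lists with "A list of procedures to be completed at each visit is described below". This objection lowers certainty but does not remove the conflict.

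**The preamble may already limit the rule.** It opens with "Following rule will be applied for subjects with BSA < 3 at Baseline due to missing post-Baseline measurements for BASI and PASI", which can be read as covering only visits where the data are missing. On that reading no observed value is overridden and the defect is one of drafting. The operative sentence has no such limit, so the text still needs to say which is meant.

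**The effect is minor.** This stands. MDA is one of the other efficacy variables, its time points are exploratory under protocol Section 4.1.3, and SAP 8.3 summarizes it by frequency tables. The Week 12 interim list in SAP 4.3.1 names MDA, with tables up to Week 12 and up to Week 24, but not modified MDA.

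**Stronger readings.** A reader might infer that reported MDA rates are materially inflated or that one arm is favored. The documents give neither the number of subjects whose BSA rises past 3% nor any difference between arms. A reader might also count 5 affected visits of 9 by including Early Termination and Safety Follow-Up; for the reasons shown in the working, 3 of 7 is the fair count. Nor is this an arithmetic error, since no figure in either document is wrong.

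**Conclusion.** The point holds as a low-impact inconsistency in a scoring rule. As written, SAP 8.3.1 overrides an observed BSA >3% at Weeks 12, 24 and 48 in subjects with Baseline BSA <3%. Relative to observed scoring, the shift has one direction: MDA can change from fail to pass when exactly 4 of the other 6 criteria are met, and modified MDA when 4 or more are met. The number affected is unknown and probably small.

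The conclusion assumes that the Section 8 visit lists describe what was collected and that 'always' is applied literally. If the rule was meant only for missing data, the change simply states that intent. At visits with no BSA the rule has a basis and can stay, provided that it does not overrule an earlier observed BSA >3%.

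**What to change.** In SAP 8.3.1, replace the unconditional rule with wording to this effect:

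*In subjects with Baseline BSA <3%, score the skin criterion from the observed post-Baseline BSA at every visit where BSA was measured: met if ≤3, not met if >3. Where no BSA was measured at a visit, assume the criterion is met only if the most recent observed BSA is ≤3.*

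Apply the same rule to modified MDA in 8.3.1.1, and correct BASI to BSA. The condition on the most recent value prevents a subject with BSA >3% at Week 12 from being assumed to meet the criterion at Week 16. No extra rule scoring a scheduled but missed BSA as not met is needed; that would be a new imputation choice beyond this defect.

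The text change is short and uses data that the visit lists already collect. It has two costs. First, PASI is not collected in these subjects, so someone with BSA >3% and an unmeasured PASI ≤1 would be scored as not met; the SAP should say so. Second, under SAP 4.3.1 treatment codes were to go to most sponsor personnel at the Week 12 interim, so the change comes after unblinding and interim and final MDA could differ. If interim tables used the present rule, record the change in 4.3.1.1 and 4.3.2.1, as was done for the CRP and hs-CRP Baseline definition.
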